3.1 Study Population

This study will be conducted in adults who have previously documented mutations in the gene for the GNE/MNK enzyme leading to a diagnosis of GNEM (variously termed HIBM, DMRV, or Nonaka disease). These patients have an impaired ability to synthesize endogenous SA, which leads to muscle weakness and atrophy. Consequently, this is the relevant population for testing SA replacement therapy, and for determining if SA replacement leads to improved protein and lipid sialylation and stabilized or improved muscle structure and performance.

Individuals who have ingested N-acetyl-D-mannosamine (ManNAc) or similar other SA-producing compounds during the 60 days prior to the Screening Visit will be excluded as it could confound interpretation of the results.

3.2 Dosage and Administration

Each Ace-ER tablet contains 500 mg of SA in an extended release formulation for a total weight of 1200 mg/tablet. The drug will be administered by the oral route and will be divided into a TID regimen: 4 tablets taken in the morning, early evening, and before bedtime (qHS). The dose should be taken with food (i.e., within 30 minutes after a meal or snack).

Treatment will be administered for a total of 24 months (96 weeks).

3.3 Blinding and Randomization Methods

This is open-label extension study consists of one treatment arm. All subjects will be treated with Ace-ER 6 g/day. Randomization and blinding are not applicable.

3.4 Stratification Factors

No stratification factors are planned.

3.5 Sample Size Considerations

The current study is primarily designed to evaluate safety and the sample size is intended to provide the maximum amount of information regarding UX001 tolerability along with indicators of long-term safety and efficacy in this patient population. Approximately 180 adult subjects with GNEM are expected to roll-over from UX001-CL202, UX001-CL301, and UX001-CL203 studies to participate in this extension study.

3.6 Interim Analysis

No interim analysis is planned for this study.

3.7 Data Monitoring Committee

No formal DMC is planned for this study in the protocol. Conduct of the study and safety of the patients will be monitored by Ultragenyx on a regular basis.

4 STUDY ENDPOINTS AND COVARIATES

All data are collected according to the schedule of assessments (Appendix [10.4](#)).

Overall safety endpoints serve to evaluate the long-term safety of 6 g/day Ace-ER treatment in subjects with GNE Myopathy (primary objective).

Overall efficacy endpoints serve to evaluate the long-term effect of 6 g/day of Ace-ER treatment in subjects with GNEM.

4.1 Safety Endpoints

4.1.1 Primary Safety Endpoint

The primary endpoint of the study is the incidence and frequency of AEs and SAEs assessed as related to Ace-ER over the duration of the study.

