**ENDPOINTS:**

**Overall Safety Endpoint (Primary Endpoint):** Evaluate the long-term safety of 6 g/day Ace-ER treatment in subjects with GNE Myopathy

**Overall Efficacy Endpoints:** Evaluate the long-term effect of 6 g/day of Ace-ER treatment in subjects with GNEM. Efficacy will be evaluated as follows:

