**Figure 7.1.1: Study Schema**

## 7.2 Discussion of Study Design

This Phase 3b study is designed to be a long-term safety and efficacy study of 6 g/day Ace-ER in GNEM patients. The study will assess long-term effects of Ace-ER on clinical measures of muscle strength, mobility, function, ability and health-related quality of life. The primary endpoint of the study is safety.

The treatment duration of up to 24 months is intended to evaluate the long-term safety and efficacy of Ace-ER. The study is limited to GNEM patients who have completed UX001-CL202 (open label, safety study in GNEM patients), UX001-CL301 (randomized, double-blind, placebo-controlled, Phase 3 study), or UX001-CL203 (open label, safety study in GNEM patients with severe ambulatory impairment).

The study will assess the safety of the study drug by the incidence and frequency of adverse events and serious adverse events. Any significant changes from baseline to scheduled time points in concomitant medications, physical examination results, vital signs, clinical laboratory test results, interval history, and C-SSRS will also be part of the safety evaluation.

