#### **7.6.6 Safety Analyses**

Safety will be evaluated for the overall study population as well as for subjects from the UX001-CL202, UX001-CL301, and UX001-CL203 study.

The safety analysis set will be used for the analyses of all safety endpoints. Safety will be evaluated by the incidence, frequency and severity of AEs and SAEs, and clinically significant changes from study baseline to scheduled time points in:

- Interval history
- Vital signs
- Physical examination findings
- Clinical laboratory evaluations
- Suicidal ideation and behavior assessments (C-SSRS)
- Concomitant medications

All AEs will be coded using the Medical Dictionary for Regulatory Activities (MedDRA). The incidence and frequency of AEs will be summarized by System Organ Class (SOC), Preferred Term (PT), severity, and relationship to treatment. The numbers (frequency) and incidence rates of AEs and SAEs will be summarized by treatment group. A by-subject listing will be provided for those subjects who experience a SAE, including death, or experience an AE associated with early withdrawal from the study or study drug treatment.

Clinical laboratory data will be summarized by the type of laboratory test. The frequency and percentage of subjects who experience abnormal clinical laboratory results (i.e. outside of reference ranges) and/or clinically significant abnormalities will be presented for each clinical laboratory measurement. For each clinical laboratory measurement, descriptive statistics will be provided for study baseline and all subsequent post-treatment scheduled visits. Changes from study baseline to the post-treatment visits will also be provided.

Changes in findings from study baseline physical examinations will be tabulated for each subject by examination category. If there are examination findings that change in more than one subject, these will be tabulated in a separate table and expressed as the number of subjects with the change out of the total. No statistics will be applied to the physical examination findings.

The SAP will provide additional details on the planned safety analyses.

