1 INTRODUCTION

The purpose of this Statistical Analysis Plan (SAP) is to provide details of the statistical analyses that have been outlined within the UX001-CL302 original protocol dated 10 February 2016 and the UX001-CL302 Protocol Amendment 1 dated 17 June 2016. Should there be a difference between the SAP and the protocol with respect to analysis methods, the SAP will take precedence over the protocol.

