3 STUDY DESIGN

This open-label extension study will assess the long-term safety and efficacy of Ace-ER treatment over a period of 24 months. Approximately 180 subjects from the UX001-CL202, UX001-CL301, and UX001-CL203 studies will be eligible to enroll in the study.

Subjects will take 4 tablets (500 mg Ace-ER each for 2 g per dose) orally 3 times per day (TID). The dose should be taken with food (i.e. within 30 minutes after a meal or snack). Subjects being treated with 12 g/day Ace-ER in UX001-CL202 will be transitioned to 6 g/day Ace-ER dose in this protocol. Treatment will be administered for a total of 24 months. Study visits will occur every 8 weeks for 24 weeks and then every 6 months for subjects enrolling from UX001-CL202 or UX001-CL301. For subjects enrolling from UX001-CL203 studies, study visits will occur every 6 months. The schedule of assessments is shown in Appendix 10.4.

[figure not shown]
Safety will be evaluated by review of the incidence and frequency of AEs and SAEs and clinically significant changes in interval history, physical examination results, vital signs, clinical laboratory test results, the Columbia Suicide Severity Rating Scale (C-SSRS) (Posner et al. 2011), and concomitant medications.

Blood samples will be collected to evaluate biomarkers (for example sialylation of serum proteins before and after treatment) to determine their utility in predicting clinical outcomes.

Efficacy will be evaluated based on assessments used in the parent study from which subjects roll over (subjects enrolling from UX001-CL202 will follow the same schedule of events as subjects who roll over from UX001-CL301), and include dynamometry as a measure of muscle strength and patient- and clinician-reported outcome measures as indicators of physical functioning and quality of life. For UX001-CL202 subjects, assessments that cannot be safely performed by a subject due to disease progression should not be administered.

A study schema demonstrating the enrolling patient populations and scheduled study visits is shown in Figure 3.1.

Figure 3.1: Study Schema

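### SAP 4.1.1 limits the primary safety endpoint to events judged related to Ace-ER; the protocol and SAP section 3 set no such limit

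*SAP*

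**What the plan says.** The protocol labels its primary endpoint in general terms: "Evaluate the long-term safety of 6 g/day Ace-ER treatment in subjects with GNE Myopathy" (Synopsis, repeated in 6.1), and in 7.2 "The primary endpoint of the study is safety". It then says how safety is measured. Section 7.2: "The study will assess the safety of the study drug by the incidence and frequency of adverse events and serious adverse events". Section 7.6.6: "Safety will be evaluated by the incidence, frequency and severity of AEs and SAEs", together with clinically significant changes in laboratory results, vital signs, examinations, C-SSRS, interval history and concomitant medications. Relationship to treatment appears in 7.6.6 only as one of the ways AEs are tabulated.

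SAP section 3 stays with the unrestricted measure: "Safety will be evaluated by review of the incidence and frequency of AEs and SAEs". SAP 4.1.1 does not. There the primary endpoint is "the incidence and frequency of AEs and SAEs assessed as related to Ace-ER". SAP 4.1.2 then lists the other safety endpoints: the same non-AE measures, plus drug concentrations and urine ManNAc.

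**The concern.** The restriction in 4.1.1 has no counterpart in the protocol or in the SAP's own design section, and neither document explains it. It matters because of how relatedness is decided. Under Protocol 8.5.3 the investigator judges it. The study has one open-label arm (SAP 3.3) and no formal DMC (SAP 3.7), so there is no blinding and no concurrent comparator against which to check the judgement. An event put down to the underlying myopathy leaves the formal primary endpoint.

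This route is not hypothetical. Protocol 5.2.4 reports that mild transaminase elevations were thought most likely to come from the muscle disease. That attribution may well be right, but it shows the kind of event the restriction can remove. What is at stake is which figure counts as the primary result of a study designed mainly to evaluate safety.

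**Working it through.** No stated figure belongs to this point: the primary endpoint has no margin, effect size, alpha or power to reproduce. The check is a comparison of texts, followed by one scale calculation.

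**1. Definitions side by side**

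| Place | What is counted | Limited to related events? |
|---|---|---|
| Protocol Synopsis, 6.1 | Long-term safety (labelled primary) | No |
| Protocol 7.2 | AEs and SAEs, plus other measures | No |
| Protocol 7.6.6 | AEs and SAEs with severity, plus other measures | No |
| SAP 3 | AEs and SAEs, plus other measures | No |
| SAP 4.1.1 (labelled primary) | AEs and SAEs, without severity | Yes |
| SAP 4.1.2 (other endpoints) | Non-AE measures, drug concentrations, ManNAc | All-cause AEs not listed |

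SAP 4.1.1 therefore differs from the protocol and from SAP section 3. Taking 4.1.1 and 4.1.2 together, all-cause AEs and SAEs have no endpoint status at all, and severity drops out of the definition.

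**2. What counts as related.** Protocol 8.5.3 groups possibly, probably and definitely related as related, and unlikely related with unrelated, for regulatory reporting. SAP 4.1.1 does not say which categories it uses. SAP 7.2.4 sets a missing causality to definitely related for events starting on or after first dose.

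**3. What will be tabulated.** SAP 8.7.1 summarises subjects with any TEAE by SOC, PT, severity, grade, outcome and relationship. The example overall TEAE table in SAP 10.7 opens with all TEAEs and maximum severity, and has a later row for subjects with related TEAEs. It has rows for serious TEAEs but, as shown, none for related serious TEAEs, although SAP 8.7.1 lists treatment-related SAEs and 4.1.1 makes them part of the primary endpoint.

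**4. Scale of the SAE part.** Protocol 5.2.4 reports no treatment-related SAEs over 2.5 years of observation. Suppose that continues. The SAE part of the endpoint is then 0 of N. The exact one-sided 95% upper bound for zero events is 1 − 0.05^(1/N):

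- N = 165 (Protocol 7.6.1: 55 + 80 + 30): 1 − 0.05^(1/165) = 0.0180, or 1.8%.
- N = 180 (SAP 3.5): 1 − 0.05^(1/180) = 0.0165, or 1.7%.

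Both results are the same however many SAEs of any cause occur, because the all-cause count does not enter the formula.

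**The case against.** The strongest reply is that this is a mismatch of wording with little practical effect. All TEAEs are tabulated and come first in the example template. Safety reporting is descriptive (SAP 8.7), and no test or decision threshold hangs on the endpoint. Missing causality is imputed conservatively. Gastrointestinal and liver-related terms get their own incidence tables (SAP 8.7.1.1) with no relatedness limit stated. An all-cause rate from a single arm does not identify drug-caused harm either.

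Most of this stands, and it limits the point. It does not remove it: imputing missing judgements does not correct biased ones, and planned tables do not settle which result is primary.

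A reader might infer four stronger things that the documents do not support:

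- That the protocol defines its primary endpoint as all AEs and SAEs. No sentence says so. The label is safety, and AEs and SAEs are among the measures.
- That the SAP demotes all-cause events in reporting, or that related events will be the headline. The SAP ranks no table, and the template leads with all TEAEs.
- That the SAP's precedence clause settles the matter. It reads "Should there be a difference between the SAP and the protocol with respect to analysis methods, the SAP will take precedence over the protocol". Whether an endpoint definition is an analysis method is arguable. If it is, the primary measure is narrowed without explanation; if it is not, two definitions coexist. Reconciliation is needed either way.
- That a given share of drug-caused events will be missed. The documents give no all-cause AE rate for this study and no accuracy of attribution, so any such percentage would be assumed.

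**Conclusion.** The discrepancy is real and lies in the primary endpoint. SAP 4.1.1 makes the formal primary result depend on unblinded investigator attribution in a single-arm study, against the protocol's unrestricted measure and the SAP's own section 3, and it leaves all-cause AEs and SAEs outside both endpoint lists. The fault concerns definition and formal status; it does not concern missing data or statistical error rates.

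The effect on the reported incidence cannot be quantified from the documents. The zero-event result (upper bound 1.8% at N=165, 1.7% at N=180) assumes that no SAE is judged related and that all planned subjects are treated. The remark about the template assumes that the example table as shown is complete.

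**What to change.** In SAP 4.1.1, define the primary endpoint as the incidence, frequency and severity of all AEs and SAEs, summarised as TEAEs as SAP 8.7.1 defines them, and report related AEs and SAEs as a subset. Add a row for related serious TEAEs to the overall TEAE template. If the sponsor prefers the restricted endpoint, the SAP should state and justify the departure from the protocol, align section 3, and list all-cause AEs and SAEs in 4.1.2.

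The link to 8.7.1 should be explicit because TEAEs are narrower than the protocol's AE collection. Protocol 7.5.5.9 and 8.5.4.1 record events from consent and review those continuing from the parent study; SAP 8.7.1 counts events starting on or after first dose and excludes continuing ones unless they worsen. The AE listings already planned in 8.7.1 can carry the remainder.

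The cost is one sentence and one table row, with no new data. The downside is that the formal primary incidence will be higher and will include events not caused by the drug, so the related subset should be shown beside it.

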4.1.2 Other Safety Endpoints

Other safety endpoints include clinically significant changes from baseline to scheduled time points in the following:

- Interval History
- Vital signs
- Physical examination results
- Clinical laboratory results
- C-SSRS (a measure of suicidal ideation and behavior)
- Concomitant medications

Drug concentration endpoints will be evaluated for the following:

- Changes from baseline in free SA level in serum;
- Changes from baseline in urine SA level;
- Frequency and percentage of subjects with the presence of ManNac detected from urine testing.

4.2 Efficacy Endpoints

Efficacy evaluations will be based on the parent study (UX001-CL202, UX001-CL301, or UX001-CL203) from which the subjects enroll. Subjects enrolling from UX001-CL202 follow the same schedule of visits for the efficacy assessments as subjects who roll over from UX001-CL301. Subjects enrolling from UX001-CL203 follow a different schedule of visits.

For subjects enrolling from UX001-CL202 and UX001-CL301:

Primary Clinical Efficacy Endpoint:

- Changes from baseline in upper extremity composite score (UEC) based on bilateral strength recorded in the following muscle groups: gross grip, shoulder abductors, elbow flexors, and elbow extensors as measured by dynamometry. The UEC is derived from the sum of the average of the right and left total force values (measured in kg);

Secondary Clinical Efficacy Endpoints:

- Changes from baseline in the scores on the mobility domain of GNEM-FAS;
- Change from baseline in the scores on the upper extremity domain of GNEM-FAS;
- Changes from baseline in lower extremity composite score (LEC) based on bilateral strength recorded in the following muscle groups: knee flexors, hip flexors, hip extensors, hip abductors and hip adductors as measured by dynamometry. The LEC is derived from the sum of the average of the right and left total force values;
- Change from baseline in the number of stands in the Sit-to-Stand test;
- Changes from baseline in the number of lifts in 30 second weighted arm lift;
- Changes from baseline in meters walked in 6MWT and percent predicted distance based on normative data for age and gender;
- Changes from baseline in total force and percent predicted total force in the Knee Extensors. The percent predicted total force value will be determined based on reference equations adjusting for age, gender, height, and weight.

Tertiary Efficacy Endpoints:

- Changes from baseline in UEC and LEC percent predicted based on reference equations adjusting for age, gender, height, and weight;
- Changes from baseline in bilateral total force and percent predicted total force for each individual muscle group included in the UEC and LEC;
- Changes from baseline in the score on self-care domain on GNEM-FAS;
- Changes from baseline in the total score on GNEM-FAS;
- Change from baseline in the total score from a 45-item self-report questionnaire (INQoL) on the impact of key muscle disease symptoms on the ability to perform basic activities of daily living, functional independence, relationships and overall well-being;
- Changes from baseline in CK levels in serum to assess the degree of reduction of CK levels observed as a surrogate for muscle injury.

For subjects enrolling from UX001-CL203:

Primary Clinical Efficacy Endpoints:

- Changes from baseline in the mobility domain of GNEM-FAS Expanded Version;
- Changes from baseline in the upper extremity domain of GNEM-FAS Expanded Version;
- Changes from baseline in the self-care domain of GNEM-FAS Expanded Version;
- Changes from baseline in the total scores of GNEM-FAS Expanded Version;
- Changes from baseline in upper extremity muscle strength and percent predicted in the following muscle groups: grip, key pinch, shoulder abductors and wrist extensors as measured by HHD
- Changes from baseline in lower extremity muscle strength and percent predicted in the knee extensors as measured by HHD

Exploratory endpoints:

- Changes from baseline in 8 subscales and summary scores (PCS and MCS) in health-related quality of life as assessed by using Short Form Health Survey – 36 (SF-36v2);
- Changes from baseline in creatine kinase (CK) and serum aceneuramic acid.

Assessments, upon which efficacy endpoints are based on, are shown in [Table 4.2.1](#). Detailed information on efficacy endpoints and visit schedules by study can be found in [Appendix 10.1](#).

Table 4.2.1: Efficacy Assessments Performed by Parent Study

	CL202 and CL301	CL203
Assessment	Week 0, 8, 16, 24, 48, 72, 96	Week 0, 24, 48, 72, 96
Functional	HHD* 6MWT Sit-to-Stand Test Weighted Arm Lift Test GNEM FAS	HHD^ GNEM FAS expanded version
QoL Questionnaire	INQoL	SF-36 short form
Biomarker	CK Free serum SA Urine ManNAc	

* Measured by HHD, the Upper Extremity Composite (UEC) Score is based on gross grip, shoulder abductors, elbow flexors, and elbow extensors. The Lower Extremity Composite (LEC) Score is based on knee flexors, hip flexors, hip extensors, hip abductors, and hip adductors.

^ Measured by HHD, UEC is not defined in this study for analysis, since different muscle groups from the other two studies are measured. Lower extremity muscle strength of knee extensors is included.

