- GNEM-FAS – Expanded Version: Physical functioning will be assessed using a disease-specific, self-reported outcome measure. Scores on the mobility, self-care and upper extremity domains of the GNEM-FAS Expanded Version will be analyzed separately as secondary variables
- Upper Extremity Muscle Strength: Muscle strength measured as the maximum voluntary isometric contraction (MVIC) against a dynamometer will be measured bilaterally in the following upper extremity muscle groups: grip, key pinch, shoulder abductors and wrist extensors. A UEC, will be derived as the sum of the average of the right and left total force values (measured in kg) when force values are available for all muscle groups tested
- Lower Extremity Muscle Strength: Muscle strength based on the maximum voluntary isometric contraction (MVIC) against a dynamometer will be measured bilaterally for the knee extensors in subjects that can be positioned for testing.

Exploratory Variables:

- Short Form Health Survey-36 (SF-36): Quality of life will be assessed using the SF-36 with scores reported for the Physical Component Summary, Mental Component Summary and the eight subscales, including physical functioning, role-physical, bodily pain, general health, social functioning, role-emotional, vitality, and mental health
- Biomarkers: Serum will be obtained at all study visits to evaluate CK, serum aceneuramic acid, and potential biomarkers of sialylation and other markers of muscle injury and remodeling

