5.2 Subgroup

The following subgroups are defined for this study:

- Gender (Male and Female)
- Age (above and below median)
- Ethnicity (small groups may be combined)
- Genetic Mutation
 - Genotype: Homozygote, Heterozygote, and Compound Heterozygote
 - Mutation type: Exon and Intron

Genetic mutation subgroup analysis will be done for the following primary efficacy endpoints: the changes from baseline in UEC score in subjects enrolled from CL301 and CL202; and the changes from baseline in lower extremity muscle strength of knee extensors in subjects enrolled from CL203.

Gender, age, and ethnicity subgroup summaries will be done to support the safety.

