8 STATISTICAL METHODS OF ANALYSES

8.1 General Principles

All statistical tests will be two-sided and a difference resulting in a p-value of less than or equal to 0.05 will be considered statistically significant. All p-values will be rounded to and displayed in four decimals. If a p-value less than 0.0001 occurs, it will be shown in the table as <0.0001.

Continuous variables will be summarized by number of subjects and mean, SD/SE, median, minimum, and maximum values. Categorical variables will be summarized by number and percentage. No imputation on missing data will be made, unless stated otherwise.

Data collected will be presented in listings. Data not subject to analysis according to this plan will not appear in any tables or graphs but will be included in the data listings.

Post-hoc exploratory analyses not identified in this SAP may be performed to further examine the study data. These analyses will be clearly identified as such in the final clinical study report. The SAP will not be amended for post-hoc or additional analyses identified after planned analyses are completed. Similarly, additional tables and figures may be defined to further evaluate study results and the SAP will not be amended to list them.

Efficacy analyses will be presented by the parent study as illustrated in [Table 8.1.1](#): UX001-CL301, CL202 or CL203. Different efficacy endpoints at different scheduled time points were collected depending on which parent study the subjects were enrolled from.

Safety analyses will be presented by the parent studies and overall as illustrated in [Table 8.1.1](#). Subjects enrolling from UX001-CL301 will be further examined by the treatment group assigned in the parent study: placebo, Ace-ER 6 g/day, and All.

[Table 8.1.1](#) also provides the guidance for the treatment groups to be displayed for biomarker analyses as well as efficacy analyses and safety analyses, which have been described above. Baseline used for the analyses are specified as well. Example table templates are provided in [Appendix 10.6](#) for efficacy and safety.

Table 8.1.1: Analysis Presentation

Analysis Category	Analysis Set	Parent Study	Treatment Group	Baseline Applied	
Week 96/ET efficacy analysis	Full Analysis Set	CL301	Placebo*	Parent Study Baseline	
			Ace-ER 6 g/day		
			Placebo*	Current Study Baseline	
			ACE-ER 6 g/day		
			All		
Week 96/ET efficacy analysis	Full Analysis Set	CL202	Ace-ER 6 g/day	Current Study Baseline	

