8.6 Efficacy Analysis

Efficacy analyses will use generalized estimating equation (GEE) (Hanley et al. 2003) to evaluate trends over time with respect to the changes from baseline for all continuous efficacy endpoints. Baseline will be included as a covariate in the model. GEE will be the primary analysis method for all repeated measures endpoints. The statistical analyses will be reported in summary tables, figures, and data listings. Statistical tests will be 2-sided at the alpha=0.05 significance level.

Efficacy analysis will be based on the full analysis set.

Additional efficacy analyses may be performed for subjects enrolled in CL301 by incorporating data from both the parent study and the current study to compare the placebo versus UX001 treatment groups using the methodology described in ([Hu et al. 2007](#)). Such analyses examine the extended treatment effect of UX001 on the placebo subjects who now are taking UX001 in the extension study.

Parent study baseline will be used to evaluate the long-term study drug effect from the parent study drug administration, except for subjects enrolling from CL202.

Current study baseline will be used to evaluate the continuous long-term study drug effect going on after the parent study.

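### For CL203 the SAP makes 14 correlated variables primary, on two baselines, each at 0.05 with no multiplicity rule, while the protocol ranks most of them lower and names no CL203 primary

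*SAP*

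**What the plan says.** **SAP.** Section 4.2 gives the CL203 cohort a plural list headed "Primary Clinical Efficacy Endpoints". It has six bullets. Four are GNEM-FAS Expanded scores, one for each of the three domains and one for the total. The fifth bullet reads "Changes from baseline in upper extremity muscle strength and percent predicted in the following muscle groups: grip, key pinch, shoulder abductors and wrist extensors", by dynamometry. The sixth does the same for the legs, in one muscle group only: "Changes from baseline in lower extremity muscle strength and percent predicted in the knee extensors as measured by HHD". There is no CL203 secondary tier; the next heading is exploratory. Appendix 10.1 repeats the labels, marking the same FAS and dynamometry rows as primary and assigning them a GEE model.

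Table 8.1.1 lists both the parent-study and the current-study baseline for CL203, and Section 8.6 exempts only CL202 from the parent baseline. On testing, Section 8.6 says "Statistical tests will be 2-sided at the alpha=0.05 significance level", and Section 8.1 says "a difference resulting in a p-value of less than or equal to 0.05 will be considered statistically significant". Neither document gives a multiplicity adjustment or a testing order.

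**Protocol.** The synopsis (Efficacy, UX001-CL203) heads its list simply as clinical efficacy variables and names none as primary. It says the three FAS Expanded domain scores "will be analyzed separately as secondary variables". Section 7.5.2.1 places strength and percent predicted for each muscle group at secondary or tertiary level. Section 7.6.4 defines one baseline.

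**The other cohorts.** For CL202 and CL301, SAP 4.2 has a single primary efficacy endpoint, the UEC. There the FAS total, FAS self-care, and individual-muscle force and percent predicted for the UEC and LEC groups are tertiary, with summary statistics only in Appendix 10.1. The counterparts of these measures are primary with GEE for CL203.

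**The concern.** When every main efficacy variable in a cohort is primary, the word no longer restricts anything. As the SAP stands, one favourable result among the CL203 set, on whichever baseline, could be reported as a statistically significant primary efficacy endpoint without departing from the plan. The protocol does not settle the matter: it offers no CL203 primary and ranks most of these variables lower than the SAP does. What is at stake is how an open-label, single-arm efficacy result is described in the study report.

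**Working it through.** **1. Plan figures.** Protocol 7.6.1 gives cohorts of 55 + 80 + 30 = 165, which reproduces its total; CL203 is the 30. The SAP says about 180 without a split. Neither document states a family-wise error rate, so there is none to reproduce.

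**2. Count of variables.** FAS Expanded: 3 domains + total = 4. Upper extremity: 4 muscle groups × 2 scales = 8. Knee extensors: 1 × 2 = 2. Total 4 + 8 + 2 = 14; with two baselines, 14 × 2 = 28.

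This count assumes one test per variable and baseline. The SAP states no null hypothesis or contrast for the GEE, and the CL203 template in Appendix 10.7 shows only descriptive statistics. By-visit tests would add to the count.

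**3. Upper reference, independent tests.**
- 14 tests: 1 − 0.95^14 = 0.51
- 28 tests: 1 − 0.95^28 = 0.76

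**4. Why independence does not apply.**
- The FAS total is built from its domains (SAP 10.2 requires all three).
- Percent predicted is observed force over predicted normal force (SAP 10.3), and protocol 7.5.5.3.1 fixes the height and weight inputs at baseline. Five of the 14 are therefore close to rescaled copies of five others.
- Changes from the two baselines share the same follow-up values.

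**5. Allowing for this structure.** The simulation used n = 30 and zero true mean change, with 6,000 runs per setting. It took eight distinct constructs (three domains, five muscle groups) with a common correlation, the FAS total as the sum of domains, and percent predicted as force divided by a subject constant. Changes on the two baselines were correlated at 0.5 to 0.9. Each test was a two-sided one-sample t test at 0.05. The documents give no correlations, so these are assumptions shown as a range.

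| Correlation between constructs | 14 tests, one baseline | 28 tests, two baselines |
|---|---|---|
| 0 | 38-40% | 52-60% |
| 0.3 | 34-35% | 45-55% |
| 0.5 | 29-30% | 38-46% |
| 0.7 | 21-23% | 29-38% |
| 0.9 | 13-14% | 18-24% |

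Entries are the chance of at least one p≤0.05. The spread for 28 tests is mainly the baseline correlation; the spread for 14 tests is simulation error (standard error at most √(0.25/6000) = 0.6 percentage points).

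**6. Favourable direction only.** Under independence: 1 − 0.975^14 = 0.30 and 1 − 0.975^28 = 0.51. With the dependence above: about 7-21% for 14 tests and 9-36% for 28, against 2.5% for one test.

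**7. Role of the sample size.** Multiplicity does not depend on n. A small n matters only if the GEE uses an uncorrected variance: mimicking that with Wald z tests at n = 30 put each single test at about 6-7%. The SAP names no small-sample correction.

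**The case against.** The strongest reply is that nothing confirmatory rests on these results. The primary endpoint is safety (SAP 4.1.1), efficacy is a secondary objective (SAP 2.2), and the sample size is meant to inform tolerability with indicators of efficacy. The two baselines also answer different stated questions (SAP 8.6): effect since parent-study dosing, and continuing effect afterwards. This stands, and it limits the consequence to reporting. It does not explain why the SAP attaches both a primary label and a significance rule to the whole set.

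A second reply is that zero mean change is a generous null. GNEM is progressive, so an ineffective drug would be expected to show decline, and a significant decline could not be presented as a benefit. This also stands: the favourable-only figures are the relevant ones for a spurious benefit claim, and true decline would lower them further.

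A third is that SAP Section 1 gives the SAP precedence. That clause concerns analysis methods and does not clearly cover the ranking of endpoints.

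Three stronger readings are tempting but unsupported:
- **That a CL203 false positive is likely.** The chance passes one half only with independent or weakly correlated tests and both baselines counted; the construction of the variables argues against independence.
- **That about 30 subjects creates the problem.** It does not; see step 7.
- **That SAP 5.2 names a rival primary.** For mutation subgroups it selects "the changes from baseline in lower extremity muscle strength of knee extensors in subjects enrolled from CL203". That variable is already on the 4.2 list, so choosing it for subgroup work is consistent with 4.2, although no reason for the choice is given.

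**Conclusion.** The concern holds as a labelling and reporting weakness that should be corrected. The SAP makes 14 dependent CL203 variables primary, on two baselines, with unadjusted 0.05 tests, and departs from the protocol's ranking without saying so. If true mean change is zero, the chance of at least one nominally significant result is roughly 14-40% for 14 tests and 18-60% for 28, and about half that for a favourable one. The 51% and 76% figures are upper references under independence, not estimates. The ranges rest on assumed correlations of 0 to 0.9, valid single tests, and an inferred count of one p-value per variable and baseline. The exposure is selective reporting of an uncontrolled secondary result; the safety conclusion is unaffected.

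**What to change.** Before database lock, take one of two routes:
- Name one CL203 primary efficacy variable on one baseline. GNEM-FAS Expanded total is one candidate, since protocol 6.1 lists it first for this cohort, but the choice belongs to the sponsor. Relabel the rest as secondary with nominal p-values and keep the other baseline as supportive.
- Or label all CL203 efficacy as descriptive, with nominal p-values and no claim of significance.

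Either way, align SAP 4.2, 5.2, 8.6, Table 8.1.1 and Appendix 10.1, and state where and why the SAP departs from the protocol's labels in the synopsis and Section 7.5.2.1. Stating the GEE contrast to be tested would also fix the number of p-values.

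The cost is text editing. No data are lost, and a single chosen endpoint keeps its 0.05 level. The downside is that fewer CL203 results can be called primary or significant.
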